A handful of other intervention studies have addressed SSS access (Gilbert et al., 2016; 2017; Matcham et al., 2014; Murray et al., 2008), and all have used leaflets or letters from GPs to reach smokers. StopApp is a brief, novel web-based behaviour change intervention, developed with input from smokers from across the SES spectrum that targets the known barriers to service access to improve users' motivation and capability to access SSS. StopApp links to an existing on-line booking system (PharmOutcomes) to provide the opportunity to get a first appointment at SSSs at a time and location to suit the user and could be promoted and accessed across the public health system. Although leaflet and letter based methods are effective, StopApp is unique in that its systematic evidence based development (Fulton et al., 2016; see also detailed description in section 7 below), aimed to address all identified barriers to accessing SSSs whilst also taking account of (or will take account of during evaluation) affordability, practicability, effectiveness (and costeffectiveness), acceptability, side-effects (and safety), and equity (Michie, 2014). The StopApp intervention would likely be delivered at even lower ongoing cost than the cost-effective Start2quit letter and taster session (Gilbert et al 2016; 2017), and if well marketed could reach currently unreached smokers.

A future potential randomised controlled trial will enable us to establish whether and to what extent StopApp is effective and cost-effective at increasing SSS bookings and attendance in comparison to standard methods of recruitment. If effective and cost-effective, it is instantly scalable because PharmOutcomes is used extensively across the UK. Because of the novelty of this intervention, the potential for overlooking health inequalities associated with smoking when using digital interventions, and the limited extant research employing the required trial design across recruitment contexts that replicate real-world use of the intervention (including online and community settings), a feasibility trial is required to establish whether a future RCT can be done and achieved without extensively over-representing or under-representing certain demographic groups.

3. Aims and Objectives

3.1 Aim: The aim of the proposed research is to establish the feasibility and potential health equity of a future randomised controlled trial of the StopApp intervention.

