3.3 Secondary Objectives

Secondary objectives of the feasibility trial are to estimate the:

- **3.3.1** acceptability of randomisation and the StopApp intervention for participants
- **3.3.2** acceptability of primary and secondary outcome measures and measures required for cost-effectiveness and cost utility analyses in a future trial
- **3.3.3** key costs which would be incurred in delivering the intervention and usual care, including a comparison of non-attendance at SSS (Did-not-attend or DNA rates) between each arm of the trial.
- **3.3.4** feasibility of accessing SSS and GP data (if recruited via GP) on attendance, quit dates set and four-week quits for trial participants
- **3.3.5** any differential recruitment and attrition rates across socio-economic groups and age and gender
- **3.3.6** rate of SSS attendance in the treatment and control groups to estimate the event rate of the primary outcome measure for a future trial and support future trial sample size calculations

4. Methodology

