4.11 Estimated recruitment rate and proposed sample size

The primary objective of this study is to assess the feasibility of recruitment to a potential future definitive RCT and therefore formal power analysis is not appropriate. However, in order to determine the target sample size we have drawn on two sources. Teare et al. (2014) recommend that external pilot and feasibility studies with binary outcome measures (in this case attend vs. does not attend SSS) recruit at least 60 participants in each group (minimum N=120) and a maximum of 100 participants in each group (maximum N=200). In addition, our sample size calculations, based on similar definitive RCT data about recruiting smokers to trials via letters from their GPs, suggested that we would need to enrol 980 smokers to detect a 7% difference between control and intervention arms in a definitive trial. Based on this estimate, any trial would need to recruit 1.8 participants per day to achieve the required recruitment in 18 months. We plan to recruit for three months, and based on needing to recruit 1.8 participants per day, we need to reach a required sample size of **162** participants (54 per setting). With a sample size of 162, the recruitment rate of smokers for a full RCT will be estimable with a precision (95% CI width) of +/- 5%.

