4.12 Statistical analysis plan

Feasibility and acceptability of all measures will be assessed by level of completeness and by follow-up qualitative interviews with a sub-sample of participants (see detail above on nested qualitative study). We will calculate recruitment rate via GP surgeries as a percentage of those recruited from those smokers identified on participating GPs lists. We will calculate recruitment via community and online settings as the time taken and spend required to recruit 54 participants and/or the number recruited and spend over three months. We will

calculate the average recruitment rate per day across the three settings. We will provide percentage rates for attrition across each recruitment setting at each of baseline, intervention/control access, and two-month follow-up.

We will look at the observed difference between intervention and control groups for bookings and attendance at SSS and use this data to support estimates for the required sample size for a definitive trial. Clinical significance will also be used in these estimates and a comparison of the two will help to determine future trial feasibility. We will assess level of completeness of all measures and run missing value analysis to determine whether any missing data are missing at random or whether patterns of missing data may indicate a problem with measures.

We will report observed and self-reported bookings, attendances, quit rates set and four-week quits across the intervention and control groups, and the proportion of participants agreeing to allow access to SSS and GP data (where relevant) relating to smoking status and SSS attendance.

We will report on numbers of higher versus lower SES status participants recruited as well as age and gender, and assess using chi-squared analysis whether SES status, age or gender are associated with attrition at baseline, intervention/control access and two-month follow-up.

5. Ethical Considerations

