The main purpose of the proposed feasibility study is to determine whether the main trial can be done. This will largely be determined by whether one or more of the recruitment settings is able to produce the required sample size for a future main trial. Based on the information discussed above we estimate that we need to recruit an average of at least 1.8 participants per day to make a future trial feasible. We will also use data collected about SES, age and gender of those recruited and lost through attrition to understand the health equity of the trial methodology.

7. Research Governance

The nominated sponsor for this research is [name], Associate Pro Vice Chancellor of Research at Coventry University. [name] has confirmed he is prepared to take on sponsorship of the study on behalf of Coventry University. The university has an Information Protection Unit that provides support and information to staff in ensuring they are fully compliant with all Information Governance requirements.

We have a Study Steering Committee (SSC) in place that will operate independently of the research team to assess research governance issues. This includes an independent chair, [name] who is also the public health speciality lead for the West Midlands Clinical Research Network (CRN), [name], a statistician form the Clinical Trials Unit (CTU) at the University of Warwick, members of our PPI group, [name], the tobacco control lead from Public Health Warwickshire, and [name], the tobacco control lead from Public Health England (West Midlands). The SSC will meet at project outset and shortly before each progress report is due to assess progress, data management and research governance issues. All data accessed and retrieved from the SSSs systems will be dealt with on secure servers and stored on password protected files accessible only to members of the research team. We will only seek data for those participants who have provided their expressed consent for us to do so. The outcome measures of this project are routinely collected and recorded by the IT systems in the SSS. The owners of PharmOutcomes and Outcomes4health (Pinnacle Health Ltd) have worked with us to ensure StopApp sends the relevant referral data (only name and mobile telephone number) to the system and stores no data on StopApp itself (user information) that would contravene Information Governance requirements. Instead all data is sent via a secure server to the existing Pinnacle Health system.

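### Differential attrition by SES, age and gender is to be estimated, but section 4.12 answers it only with chi-squared tests, which are weak at N=162 and give no size or interval for the gap

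*Protocol*

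**What the plan says.** Section 3.1 gives the aim as "to establish the feasibility and potential health equity of a future randomised controlled trial of the StopApp intervention". Section 3.3 frames the secondary objectives as quantities to be estimated, and item 3.3.5 is "any differential recruitment and attrition rates across socio-economic groups and age and gender".

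Section 4.12 then sets out the analysis. For these groups it says "We will report on numbers of higher versus lower SES status participants recruited as well as age and gender", and that the team will "assess using chi-squared analysis whether SES status, age or gender are associated with attrition at baseline, intervention/control access and two-month follow-up". Percentage attrition is promised at each stage, but broken down by recruitment setting only.

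Section 4.11 sets the sample at 162 and says that "formal power analysis is not appropriate", because recruitment feasibility is the primary objective. Its one precision statement concerns another quantity: "With a sample size of 162, the recruitment rate of smokers for a full RCT will be estimable" to within 5 points either way.

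Section 6 adds that the team intends to "use data collected about SES, age and gender of those recruited and lost through attrition to understand the health equity of the trial methodology", without saying how.

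**The concern.** The objective asks how large the differences in loss are. The stated method asks only whether a difference can be told from zero. As written, 4.12 commits to no attrition rate by SES, age or gender, no difference between groups and no interval, so the p-value is the only stated output on differential loss.

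The favourable answer for equity is that groups are not lost at materially different rates. A non-significant test supports that only if the test would probably have detected a gap that matters. If it would not, a real excess loss among lower-SES smokers could pass without remark, and planning for the definitive trial could start from a mistaken view of its equity. That question is part of what the feasibility study was set up to answer.

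**Working it through.** **The plan's own figure.** 980 participants over 18 months of 30 days is 980 / 540 = 1.81 per day, stated as 1.8. Then 1.8 × 90 days = 162, and 162 / 3 settings = 54. The sample size is reproduced. It derives from a recruitment rate, and the protocol gives no power or precision for the attrition comparisons.

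**Inputs.**
- From the protocol: N = 162; SES as higher versus lower; a chi-squared test.
- Assumed, because not stated: all 162 are in the comparison; two-sided 5% level; attrition of 5-40% in the better-retained group; SES split 50:50 (81 v 81) or 30:70 (49 v 113); true gaps of 10 and 15 percentage points.

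**Formula.** With attrition p1 and p2, group sizes n1 and n2, and pooled rate p, the probability of missing the gap is approximately Φ[(1.96·s0 − |p1 − p2|) / s1], where s0 = √[p(1−p)(1/n1 + 1/n2)] and s1 = √[p1(1−p1)/n1 + p2(1−p2)/n2].

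*Example, 81 v 81, 30% v 20%:* s0 = √(0.25 × 0.75 × 2/81) = 0.0680; s1 = √(0.21/81 + 0.16/81) = 0.0676; (1.96 × 0.0680 − 0.10) / 0.0676 = 0.49; Φ(0.49) = 0.69.

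*Example, 81 v 81, 35% v 20%:* s0 = 0.0702; s1 = 0.0692; (0.1375 − 0.15) / 0.0692 = −0.18; Φ(−0.18) = 0.43.

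**Results.** Exact enumeration of all 2×2 tables, Pearson test without continuity correction; the smaller group has the higher loss in the 49 v 113 case:

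| Attrition, better-retained group | 10-point gap missed, 81 v 81 | 10-point gap missed, 49 v 113 | 15-point gap missed, 81 v 81 | 15-point gap missed, 49 v 113 |
|---|---|---|---|---|
| 5% | 42% | 43% | 15% | 18% |
| 10% | 57% | 58% | 28% | 31% |
| 20% | 69% | 71% | 43% | 48% |
| 30% | 73% | 77% | 50% | 55% |
| 40% | 76% | 78% | 52% | 58% |

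For 80% power at a 50:50 split and 10-40% attrition in the better-retained group, the total needed is 398-776 for a 10-point gap and 200-346 for a 15-point gap, against 162.

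**What an interval would show.** The 95% half-width is 1.96 × s1. For a 10-point gap at 20% v 30% with 81 v 81, it is 1.96 × 0.0676 = 0.13. At 40% v 50% with 49 v 113, it is 1.96 × √(0.25/49 + 0.24/113) = 0.17.

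**Where the data exist.** Section 4.9.2 collects gender and self-reported SES within the baseline questionnaire, and 4.10.1 randomises those who return it. The comparison can therefore be made at intervention/control access and at two months. People lost before completing baseline will largely lack these variables.

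**The case against.** The strongest reply is that this is a feasibility study which openly declines formal power analysis, that differential attrition is a secondary objective, and that intervals are commonly left to a separate analysis plan. Equity is also addressed in other ways: counts recruited by SES, age and gender, practices stratified by deprivation, and interviews that deliberately over-represent lower-SES smokers.

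Much of this stands. Low power is not in itself an error here. What remains is that the protocol itself names the method, under a heading for statistical analysis, and that method does not suit an objective worded as estimation. Counts of those recruited do not describe who is lost.

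A reader might also infer several stronger points that the document does not support:
- *That a non-significant result will be taken as equity.* No passage says so. Section 6 speaks only of understanding equity and attaches no p-value rule to it.
- *That the 43-78% miss range belongs to the planned sample.* It depends on 20-40% attrition, the assumed splits and a 5% level. At lower attrition the tests do better, especially for a 15-point gap.
- *That the tests are uninformative in both directions.* With 20-40% attrition a 20-point gap is detected about 65-80% of the time. A 37% chance of a false positive (1 − 0.95^9) would need nine independent tests, whereas the stages follow one another in the same people.
- *That an equivalence margin is required.* With truly equal attrition of 20-40%, a rule that the upper 95% limit must lie below 10 points would declare equity only 23-36% of the time. It is a confirmatory device that this study does not need.

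**Conclusion.** The point holds as a mismatch between objective and method. Objective 3.3.5 calls for estimates, and 4.12 supplies only tests of association for attrition by SES, age and gender. How weak those tests are depends on the assumptions listed in the working: over the cases tabulated, a 10-point gap is more likely missed than found except at about 5% attrition, and a 15-point gap is missed anywhere from about one time in seven to nearly three in five. The gaps of 10 and 15 points are illustrations, since the protocol names no size of concern. The risk is that non-significance could be misread; no such misreading is planned. This is an improvement that should be made, at no cost in data, and it does not threaten the primary objective.

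**What to change.** In section 4.12, replace the chi-squared commitment with wording such as: *For SES (lower v higher), age group and gender, we will report the attrition rate in each group and the between-group difference with its 95% confidence interval, at each stage where these data exist. Any chi-squared p-values are descriptive. A non-significant result will not be taken as evidence of equitable retention.* Repeat the last sentence with the equity statement in section 6. No margin or equivalence rule is needed.

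The cost is wording only, with no extra data or participants. The downside is that at 20-40% attrition the intervals will be wide, about ±13 to ±17 points for a 10-point gap, so the conclusion on equity will often be that the data are inconclusive.

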On 'joining' a project, eNgage directs participants to Qualtrics to complete baseline measures. The participant's email address is transmitted by eNgage to Qualtrics to enable auto-scheduled email invitations and reminders to be sent throughout the project at relevant time points (i.e. completion of questionnaire and access to intervention). Each participant's unique ID is also transmitted to enable all data collected within eNgage and Qualtrics to be linked (e.g. provision of consent and questionnaire responses).

The randomisation of participants to experimental conditions occurs within eNgage. After each participant has completed their baseline questionnaire within Qualtrics, eNgage will assign condition. Whilst assignment is random, the algorithm applied uses minimisation to ensure balance by factors that are likely to affect SSS access (gender, self-report socio-economic status). Data with respect to these factors is collected for each participant within the baseline questionnaire. On study set-up within eNgage, the research team specify what these factors are and their location within the baseline questionnaire (e.g. Qs1-4). eNgage retrieves this data from Qualtrics and uses it to nominate assignment. eNgage uses the participant's unique ID (sent to Qualtrics previously) to identify the individual. Each participant's response to these questions and condition assignment is additionally stored within eNgage to enable auditing of this process.

Following assignment, participants are directed to the respective intervention or control materials (both stored on the CU server). Analytics data on their use of these materials is collected by Matomo (see below). Following this, participants are directed to complete the follow-up questionnaire within Qualtrics, at 2-months after baseline.

NB. for the My Way study, there will be a number of identical eNgage project pages, one for each of the different recruitment settings. The purpose of this is to enable the unique ID created for each participant to be associated with the type of setting they were recruited from. This is necessary to assess the success of our recruitment strategy across the different settings. The URL for each page will be the only thing that is different for each project page and this will be provided accordingly for those recruited within each of the settings.

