- 1) The eNgage data (to include for each participant: full name, email address, unique participant ID, the date and time consent given, the version of the participant information details they consented to, responses to optional consent questions, responses to randomisation questions and experimental condition assignment) will be retained within eNgage for six years after the end of the study to act as a record of participant consent. This data will be retained in this full form for six years after the end of the study (in case a participant wishes to make a claim against the university in which case both proof of consent plus associated data can be provided). The name and email addresses of those who provided consent (optional) to be contacted about future eNgage studies will be copied into a new datafile (marketing opt-in datafile). This data will be shared with the eNgage lead administrator who will store this on their private password protected OneDrive folder (located on CU server).
- The survey data (baseline and follow-up questionnaire responses collected in Qualtrics) will be downloaded, postcode data removed (to anonymise), and then stored on the team's shared password protected project folder (SharePoint – access rights outlined below; located on CU server)
- 3) Postcode data (taken from baseline survey) and associated unique ID to be downloaded and stored on the research lead's private password protected OneDrive folder (located on CU server). Postcode data to be converted to IMD score. IMD score to be added to downloaded baseline survey data (linked to participant ID). Postcode data will be retained until the end of data processing (data analysed and findings reported) and then deleted.
- 4) The analytics data (from Matomo) will be downloaded and stored on the team's shared password protected project folder (SharePoint – access rights outlined below; located on CU server); NB this data is anonymised IP address masked by default.
- The project stop smoking data will be stored on the team's shared password protected project folder (SharePoint – access rights outlined below; located on CU server)
- 6) In preparation for analysis, data from 2, 3, 4 and 5 will be linked using each participant's unique ID to create the complete datafile in preparation for analysis; initially this will be within Excel format but will likely also be exported

to SPSS (all data will however remain within the shared password protected project folder)

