4.10 Questionnaire Measures

4.10.1 Baseline measures

A baseline questionnaire will include questions regarding demographic information (including age, gender, profession, ethnicity, postcode (for purposes of identifying indices of multiple deprivation score)) current smoking status, previous use of SSS, ease of internet access, and motivation to guit, measured using the one item 'Motivation to Stop Scale', MTSS (Kotz et al., 2013) and a single item Likert scale (Hummel et al., 2017). Health-related quality of life data will be collected using the EQ5D-5L instrument to inform the health economic analysis, and the ICECAP-A (ICEpop CAPability measure for Adults) instrument will be used to measure general wellbeing. In addition, we have developed a bespoke resource use questionnaire to gain insight into the costs both to individuals and to the public purse of resources accessed as a result of participation in the study or use of the Stopapp (see appendix E). Participants will be given measures online via the project website. If they register but do not complete baseline measures within two weeks we will send email reminders. Those recruited through GP practices will be sent a reminder (using same method as initially used by GP surgery) two weeks after the first communication. All smokers who agree to take part in the study and return baseline guestionnaire responses will be randomised into either the intervention or control group as described above.

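### Protocol 4.12 tests age and socio-economic status against attrition by chi-squared, which forces finer data into unstated categories; logistic regression would be a cheap gain in power if the gradient is moderate and roughly monotone

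*Protocol*

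**What the plan says.** Protocol 4.12 names the test: the team will "assess using chi-squared analysis whether SES status, age or gender are associated with attrition at baseline, intervention/control access and two-month follow-up". The same sentence begins with a descriptive report: "We will report on numbers of higher versus lower SES status participants recruited as well as age and gender".

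The inputs are collected in what may be finer form. Section 4.10.1 states: "A baseline questionnaire will include questions regarding demographic information (including age, gender, profession, ethnicity, postcode", and gives the deprivation index as the reason for asking for postcode. Section 4.9.2 (downloaded data, step 3) adds: "Postcode data to be converted to IMD score. IMD score to be added to downloaded baseline survey data". A second socio-economic measure also exists. Section 4.9.2 lists the minimisation factors as those "likely to affect SSS access (gender, self-report socio-economic status"; the scale of that self-report is not shown.

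The analysis serves secondary objective 3.3.5, to estimate "any differential recruitment and attrition rates across socio-economic groups and age and gender". Section 6 (Stop/go criteria) says, about the trial's methods: "We will also use data collected about SES, age and gender of those recruited and lost through attrition to understand the health equity". Section 4.11 regards a formal power analysis as inappropriate for this study.

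**The concern.** A contingency-table test cannot use age in years or a deprivation score as they stand. Both must be cut, which discards the ordering and spacing within each group. With more than two bands, the test also spends degrees of freedom on an unordered alternative. The protocol gives no reason for the cut and no cut-points. Naming the test is a decision made in the text. A later analysis plan could supply bands, but it could not recover the lost information without changing the test.

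Potential health equity is part of the trial's stated aim (3.1). A less sensitive test leans towards finding no differential attrition, which is the reassuring answer. With the sample size fixed, the efficiency of the test is one of the few things that can still be improved at no cost in data or participants.

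**Working it through.** **The plan's own figure.** Section 4.11: 980 / (18 × 30 days) = 1.81, stated as 1.8 per day. Then 1.8 × 90 days = 162, as stated. The protocol gives no power, significance level or effect size for the attrition comparisons.

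**Stages covered.** Age, gender and socio-economic status come from the baseline questionnaire, and randomisation follows its return (4.10.1). People lost before completing it have no such data, so no choice of test helps at that stage. The check therefore concerns intervention/control access and two-month follow-up, with n = 162.

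**Analytic check (normal covariate).** A two-group split with proportion p on one side of cut c keeps φ(c)² / [p(1 − p)] of the information. At the median this is 2/π = 0.637, equivalent to 0.637 × 162 ≈ 103 participants. A design with 80% power on the continuous scale has a standardised effect of 1.96 + 0.84 = 2.80. After a median split, power is Φ(2.80 × √0.637 − 1.96) = Φ(0.27) ≈ 61%, a loss of about 19 points. That is about the most a median split can cost a normal covariate. The corresponding maximum is about 23 points for a 70/30 split, 26 for 75/25 and 30 for 80/20.

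**Simulation (normal covariate).** Assumptions: logit-linear attrition, two-sided 5%, 4,000 replicates. Each cell gives power (%) for the continuous test / chi-squared on a median split / chi-squared on five bands.

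| OR per SD | 20% attrition | 30% attrition | 50% attrition |
|---|---|---|---|
| 1.2 | 13/10/8 | 18/13/11 | 20/16/11 |
| 1.3 | 25/18/13 | 32/23/17 | 39/28/21 |
| 1.5 | 53/36/29 | 65/46/38 | 71/53/44 |
| 1.7 | 73/53/44 | 85/65/60 | 90/73/68 |
| 2.0 | 91/75/70 | 97/85/82 | 99/91/89 |
| 2.5 | 99/93/92 | 100/97/97 | 100/99/99 |

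For OR 1.5 to 2.0 the median split loses about 8 to 20 points and five bands about 10 to 29. At OR 1.2 or 2.5 the loss is about 1 to 9.

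**Shape of the covariate.** At OR 1.65 and 30% attrition, in the same order:
- normal: 82/62/54
- uniform: 82/70/58
- right-skewed (gamma): 84/56/57

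Repeat runs agreed to within 2 points. With the skewed covariate, the median-split loss was 22 to 30 points at OR 1.5 to 1.65 and 19 to 27 at OR 1.8, over attrition of 20% to 50%. With no gradient and 30% attrition, all three tests rejected in 4.2% to 5.3% of replicates, so the gain is not bought with a higher false-positive rate.

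**A shape that reverses the ranking.** If the true effect is a step at the median (OR 2.5, 30% attrition), a linear logistic term has 56% power and the median-split chi-squared 70%.

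**The case against.** The strongest reply is that these losses are not properties of the protocol. They depend on a gradient, an attrition rate and a categorisation that the document does not state, and on a smooth logit-linear effect, which is the model being recommended. That stands. So does the step-effect example.

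The gain also shrinks if the non-linear term becomes part of the main test. At OR 1.65 and 30% attrition, a joint linear-plus-quadratic test had 72% power, against 81% for the linear term and 60% for the median split. The non-linearity check should therefore be secondary.

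The inputs are partly inferred. Section 4.12 does not say whether the socio-economic measure is the IMD score or the self-report, and the self-report may already be categorical. The response format for age is not shown. The higher-versus-lower wording describes the report of numbers recruited; a reader might infer that the test uses that same split, but the text does not say so. Chi-squared suits gender.

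The consequences are limited. The go criterion in section 6 is 1.8 participants per day, and no significance threshold is attached to the equity data. The missing-value analysis in 4.12, and interview sampling that uses retention status and favours lower socio-economic groups, give other views of drop-out. At OR 1.2 to 1.3 even the continuous test has only 13% to 39% power, so a null result would be weak evidence under either method.

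What the reply does not remove is that chi-squared is named for age and socio-economic status, that it needs categories, and that under a moderate, roughly monotone gradient it is the less efficient choice.

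**Conclusion.** The point holds as a cheap improvement to a secondary objective. At n = 162, with an assumed OR of about 1.5 to 2.0 per SD and attrition of 20% to 50%, categorising costs about 5 to 20 points of power for a median split of a normal or uniform covariate. The cost is up to about 30 with a skewed covariate or five unordered bands. For weak or very strong gradients (OR 1.2 or 2.5) it is about 1 to 9 points. A step at the cut would favour the split.

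A reader might infer that the plan forfeits a fixed amount of power, or that the go/no-go decision is compromised. The protocol supports neither: it sets no gradient, attrition rate or cut-point, and it ties no decision rule to these tests. The part about socio-economic status applies to the IMD score only if that is the measure analysed. The part about age assumes that age is recorded more finely than in broad bands.

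**What to change.** In 4.12, for intervention/control access and two-month follow-up, make the main analysis a logistic regression of attrition (yes/no) on age and IMD score as continuous terms, with gender as a factor. Report odds ratios with 95% confidence intervals, and add a quadratic or spline term as a secondary check for non-linearity. State which socio-economic measure is analysed. If it is the self-report, enter it as an ordered variable with a trend test. Keep attrition tables by higher/lower socio-economic status and by age band as description, which still shows rates by group as objective 3.3.5 asks.

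The cost is a wording change and a few lines of code, with no new data or participants. The downside is an assumption of approximate linearity on the logit scale, and an odds ratio per unit that reads less directly than two percentages. The secondary check addresses the first and the retained tables the second. The regression also separates age, gender and deprivation from one another, which single tests cannot do.
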